9 IMMUNOGENICITY AND SAFETY VARIABLES

The planned schedule of assessments is in Section 7.2.

9.1 Informed Consent Form

The investigator or designee must explain to each subject the nature of the study, its purpose, the procedures involved, the expected duration, the potential risks and benefits involved and any potential adverse events. Each subject will be informed that participation in the study is voluntary and that they can be withdrawn from participation at any time.

All subjects must provide a signed and dated informed consent at Visit 1. An informed consent form must be approved by the Institutional Review Board (IRB), Ethics Committee (EC), and/or the applicable health authorities.

9.2 Demographics / Other Baseline Characteristics

The demographic and baseline characteristic data for subjects will be collected at Visit 1. The demographics include date of birth, age, sex and ethnicity. Any pre-vaccination medical events will be recorded as medical history. Relevant history/conditions include all those present prior to the administration of study vaccine that are listed below:

- Relevant medical history,
- All current medical conditions,
- Allergy history,

Whenever possible, diagnoses but not symptoms should be recorded.

9.3 Eligibility

Eligibility should be checked by the investigator at Visit 1 before vaccination.

9.4 Administration

Take a vial of investigational vaccine, use a disposable needle and syringe to extract vaccine and intramuscularly inject it into the middle of the lateral deltoid muscle of the subject's upper arm.

Vaccine administration will be recorded, including quantity (volume and dose). The containers from which the vaccine was administered to the subjects will be retained for dose confirmation.

9.5 Safety and Immunogenicity Measurements Assessed

9.5.1 Safety Variables

9.5.1.1 Physical Examination

Complete physical examinations should be conducted by investigator/site staff at all visits. A complete physical exam will include the examination of general appearance, HEENT (head, ears, eyes, nose, throat), neck (including thyroid), lymph nodes, skin, cardiovascular, pulmonary, abdomen, neurological system and musculoskeletal/joints.

Body weight and height will be collected at Visit 1. Body weight will be measured in indoor clothing, but without shoes and blanket to the nearest 0.1 kilogram (kg). Body height will be measured in centimeters (cm).

It must be recorded when any abnormality has been found out.

9.5.1.2 Vital Sign

Systolic/diastolic blood pressure, pulse, respiratory rate, and ear temperature will be collected at all visits.

For booster vaccination visit, vital sign should be measured prior to and after vaccine administration. All subjects in each group will be monitored at least 30 minutes after vaccination, and vital signs should be recorded in CRF.

9.5.2 Clinical Laboratory Evaluation

The clinical laboratory analyses will be performed at local laboratories. Reference ranges will be supplied by the local laboratories and used by the investigator to assess the laboratory data for clinical significance and pathological changes.

Methods and timing for assessing, recording and analyzing each laboratory variable should follow local guidelines. The following laboratory safety tests will be performed:

Blood Routine

CBC, including Hb, Hct, RBC count, WBC count, WBC differential and platelet count.

Biochemistry

ALT, AST, total bilirubin, creatinine, and HbA1c

9.5.3 Pregnancy Test

Screening for urine pregnancy, using pregnancy strip, will be performed on Day 1 before vaccination and on Day 85 for WoCBP only. It is not required for postmenopausal or surgically sterilized women. A positive urine pregnancy test should be confirmed by a serum test. Pregnancy

tests may be performed more frequently per request of Institutional Review Board (IRB)/Independent Ethics Committee (IEC) or if required by local regulations.

9.5.4 Self-Evaluation/Reporting (Solicited Symptoms)

9.5.4.1 Solicited Symptoms

Information of solicited symptoms/AEs and body temperature will be collected by the subjects in the provided e-diary cards during a 7-day follow-up period after the vaccination (i.e. day of vaccination and 6 subsequent days), and reported by the investigator team. The subject should complete the assessments in the e-diary every evening.

A solicited local and general symptoms or AEs are the one whose nature or intensity is consistent with the expected AEs described and listed below.

Table 9-1 Grading for solicited adverse events at the injection site

	Mild (Grade 1)	Moderate (Grade 2)	Severe (Grade 3)	Potentially Life Threatening (Grade 4)
Pain	Do not affect physical activity	Affect physical activity	Affect daily life	Emergency room (ER) visit or hospitalization
Induration*, swelling (optional)**#	Diameter 2.5~<5 cm and does not affect or slightly affect daily life	Diameter 5~<10 cm or interferes with daily life	Diameter ≥ 10 cm or prevents daily activity	Necrosis
Rash*, Redness (optional)** #	Diameter 2.5~<5 cm	Diameter 5~<10 cm	Diameter ≥ 10 cm	Necrosis or exfoliative dermatitis
Allergic Reaction	Itching at vaccine site, no rash	Localized urticaria	Generalized urticaria; angioedema	Anaphylaxis
Cellulitis	NA	Non-injectable treatment is required (e.g., oral antibacterial, antifungal, antiviral therapy)	Intravenous treatment is required (e.g., intravenous antibacterial, antifungal, antiviral therapy)	Sepsis, or tissue necrosis, etc.

Note: *: in addition to directly measuring the diameter for grading and evaluation, the progress of the measurement results should also be recorded.

** the maximum measuring diameter or area should be used.

the evaluation and grading of induration and swelling, rash and redness should be based on the functional level and the actual measurement results, and the indicators with higher classification should be selected.

Table 9-2 Grading for solicited systemic adverse events

	Mild (Grade 1)	Moderate (Grade 2)	Severe (Grade 3)	Potentially Life Threatening (Grade 4)
Diarrhea	2 – 3 loose stools /24 hours	4 – 5 stools /24 hours	6 or more watery stools/24 hours or requires outpatient IV hydration	ER visit or hospitalization for hypotensive shock
Fatigue	Does not affect daily activities	Affects normal daily activities	Seriously affects daily activities and cannot work	Emergency Room visit or hospitalization
Nausea/Vomiting	No interference with activity or 1 – 2 episodes/24 hours	Some interference with activity or > 2 episodes/24 hours	Prevents daily activity, requires outpatient IV hydration	Life-threatening (e.g. hypotension shock)
Anorexia	Loss of appetite, but no reduction in food intake	Loss of appetite, reduced food intake	Loss of appetite and no food intake	Need for intervention (e.g. gastric tube feeding, parenteral nutrition)
Sore throat	Transient, without treatment, without affecting daily activities	Sore throat, slightly affecting daily activities	Severe sore throat that seriously affects daily activities and requires medication	
Headache	Does not affect daily activities	Transient, slightly affects daily activities and may require treatment or intervention	Seriously affects daily activities and requires treatment or intervention	ER visit or hospitalization
Cough	Transient, without treatment	Persistent cough, effective treatment	Paroxysmal cough, uncontrollable treatment	Emergency or hospitalization
Arthralgia	Mild pain without hindering function	Moderate pain; need analgesics and / or pain that impedes function but does not affect daily activities	Severe pain; need analgesics and / or pain affecting daily activities	Disability pain
Non-injection-site muscle pain	Does not affect daily activities	Slightly affect daily activities	Severe muscle pain that seriously affects daily activities	Emergency or hospitalization
Non-injection-site itching (no skin lesions)	Slightly itchy without affecting or slightly affecting daily life	Itching affects daily life	Itching makes it impossible to carry on daily life.	NA
Abnormal skin and mucosa	Erythema / itching / color change	Diffuse rash / macular papule / dryness / desquamation	Blister / exudation / desquamation / ulcer	Exfoliative dermatitis involving mucous membrane, or erythema multiforme, or suspected Stevens-

	Mild (Grade 1)	Moderate (Grade 2)	Severe (Grade 3)	Potentially Life Threatening (Grade 4)
				Johnsons syndrome
Acute allergic reaction *	Local urticaria (blister) without treatment	Local urticaria requiring treatment or mild angioedema without treatment	Extensive urticaria or angioedema requiring treatment or mild bronchospasm	Anaphylactic shock or life- threatening bronchospasm or throat edema
Syncope	Close to syncope without losing consciousness (pre-syncope)	Loss of consciousness without treatment	Loss of consciousness and needs treatment or hospitalization	NA
Acute bronchospasm	Transient; no treatment needed	Needs treatment; bronchodilator therapy returns to normal	Bronchodilator treatment cannot return to normal	Cyanosis; or intubation required
Dyspnea	Dyspnea during exercise	Dyspnea during normal activity	Dyspnea at rest	Dyspnea, requiring oxygen therapy, hospitalization or assisted breathing

* Refers to type I hypersensitivity.

The axillary temperature will be monitored every evening on day of vaccination and 6 subsequent days. If daily axillary temperature has been measured for more than one time, only the highest degree level on any day should be recorded in the e-diary card.

Table 9-3 Grading for axillary temperature

	Mild (Grade 1)	Moderate (Grade 2)	Severe (Grade 3)	Potentially Life Threatening (Grade 4)
Fever (°C)	37.3 ~ < 38.0	38.0 ~ < 38.5	38.5 ~ < 39.5	≥39.5, last more than 3 days

9.5.4.2 Unsolicited Adverse Event

An unsolicited local and general AE or symptoms are the one whose nature or intensity is NOT consistent with the expected AEs described and listed above in this protocol. Information of unsolicited symptoms/AEs will be collected until 28-day follow-up period after each vaccination (i.e. day of vaccination and 27 subsequent days) and reported at each visit.

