The Safety Set (SS) will consist of all subjects who completed two vaccinations in Phase I study enrolled into this extension study and received one booster dose of UB-612 vaccines with the same dose as Phase II study. The Safety Set is for safety evaluation in analysis.

The Full Analysis Set (FAS) will consist of subjects who completed two vaccinations in Phase I study enrolled into this extension study, received one booster dose of UB-612 vaccines with the same dose as Phase II study, and have at least one immunogenicity assessment on Day 15 or 85 after vaccination. Subjects receive prohibited medication/treatment/vaccine during pre-specified period has impact on immunogenicity may exclude from the FAS set.

The Per Protocol Set (PPS) will be a subset of FAS. PPS includes subjects who completed two vaccinations in Phase I study enrolled into this extension study, received one booster dose of UB-612 vaccines with the same dose as Phase II study, and were compliant to the protocol. Subjects who had major protocol deviations as determined by the Study Team or who received prohibited medication/treatment/vaccine during the pre-specified period leading to an impact on immunogenicity will be excluded from the PPS set. The PPS is also analysed for immunogenicity evaluation.

All safety assessments, including AEs, PEs, VS, and clinical laboratory evaluations, where indicated, will be presented using descriptive statistics for each vaccine group of UB-612. Data will be summarized for each vaccine group.

All adverse reactions within 7 days after vaccination will be summarized with numbers and percentages by study vaccine groups. The percentage of subjects with \geq Grade 3 adverse events within 7 days after vaccination will also be demonstrated by study vaccine groups. AEs till Day 85 will be presented with number and percentage by system organ class, preferred term, and study vaccine groups. The number and percentage of SAEs during the whole follow-up period (3 months) will be presented in summary table by study vaccine groups. Adverse events of special interest during the study period will be summarized with number and percentage from the mapping result by MedDRA.

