7 INVESTIGATIONAL PLAN

7.1 Overall Study Design and Plan: Description

This is an extension study to evaluate the safety, tolerability and immunogenicity of one booster dose of UB-612 COVID-19 vaccine in adults who completed two vaccinations of UB-612 vaccine 10, 30, and 100 µg in V-122 study (Phase I).

The subjects who completed two vaccinations in Phase I study will be recruited in this extension study. After the informed consent is obtained from the subject, eligible subjects will receive one booster dose of UB-612 vaccines 100 µg with the same dose which was offered in Phase II study, at least 6 months after **completing the 2-dose primary vaccination series**. This study will be carried out in three groups:

- (1) A group: 1 booster dose of UB-612 vaccine 100 µg, for subjects at UB-612 vaccine 10 µg group previously
- (2) B group: 1 booster dose of UB-612 vaccine 100 µg, for subjects at UB-612 vaccine 30 µg group previously
- (3) C group: 1 booster dose of UB-612 vaccine 100 µg, for subjects at UB-612 vaccine 100 µg group previously

In this study, there will be 3 clinical visits. Subjects will come to the clinics at Visit 1 (Day 1, baseline, booster vaccination, at least 6 months after **completing the primary vaccination series** in V-122 study), Visit 2 (Day 15), and Visit 3 (Day 85, 3 months after booster vaccination).

In all groups, an informed consent and the eligibility of subjects will be checked at Visit 1 (Day 1). The booster study vaccine administration will be done immediately after blood draw which will evaluate baseline laboratory safety and humoral / cellular immune response / SARS-CoV-2 test. All subjects in each group will be monitored at least 30 minutes after vaccination (for vital signs change and adverse events). The post-vaccination e-diary card for 7-day solicited adverse events after vaccination will be given to subjects with a suitable instruction.

At Visit 2 (Day 15), subjects will return to clinics and for laboratory safety check and have a blood drawn for humoral / cellular immune response.

At Visit 3 (Day 85, 3-month follow-up visit after booster vaccination), the subjects will return to clinics and have blood drawn for humoral immune / cellular immune response/ SARS-CoV-2 test

All adverse events and serious adverse events will be monitored from Visit 1 (Day 1) until Visit 3 (Day 85).

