8.2 Visit 2 (Day 15 ± 3 day)

The following assessment(s) must be collected/performed:

- (1) Conduct physical examination.
- (2) Measure vital signs.
- (3) Collect blood sample for following local laboratory tests:
 - Blood routine test
 - Biochemistry tests
- (4) Collect blood sample for immunogenicity tests (central laboratory)
 - Humoral immune response
 - Cellular immune response

- (5) Review concomitant medications.
- (6) Conduct COVID-19 surveillance
- (7) Record and report adverse or serious adverse event if any has occurred since the previous visit.

8.3 Visit 3 (Day 85 ± 5 days) –Month 3 Follow-up /End of Study

The following assessment(s) must be collected/performed:

- (1) Conduct physical examination.
- (2) Measure vital signs.
- (3) Perform a urine pregnancy test
- (4) Collect blood sample for immunogenicity tests (central laboratory):
 - Humoral immune response
 - Cellular immune response
- (5) Collect blood sample for SARS-CoV-2 test
 - Serum antibodies (IgG) against SARS-CoV-2.
- (6) Review concomitant medications.
- (7) Conduct COVID-19 surveillance
- (8) Record and report adverse or serious adverse event if any has occurred since the previous visit.

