9.5.5 Adverse events (AEs)

In this study, all AEs/SAEs will be recorded after vaccination.

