9.5.5.9 Adverse Events Reporting

Documentation and Reporting of Adverse Events

All investigators should follow up subjects with AEs until the event is resolved or until, in the opinion of the investigator, the event is stabilized or determined to be chronic. Details of AE resolution must be documented in the CRF.

All AEs should be reported and documented in accordance with the procedures outlined in this section. All AEs occurring during the study must be documented on the relevant CRF pages.

Reporting of Serious Adverse Events

Any SAE must be reported by the investigator if it occurs during the clinical study or within 4-7 days of receiving the study agent, whether or not the SAE is considered to be related to the investigational product. An SAE report consists of the SAE form, the AE form, and the concomitant medication form. A copy of these forms must be emailed **within 24 hours** to Contract Research Organization (CRO), StatPlus Inc., and StatPlus will inform United Biomedical, Inc., Asia on the same day.

The investigator should not wait to receive additional information to document fully the event before notification of a SAE, though additional information may be requested. Where applicable, information from relevant laboratory results, hospital case records, and autopsy reports should be obtained.

Instances of death, congenital abnormality, or an event that is of such clinical concern as to influence the overall assessment of safety, if brought to the attention of the investigator at any time after cessation of study agent administration and linked by the investigator to this study, should be reported to the study monitor.

The sponsor and/or the appointed representative(s) will promptly notify all relevant investigators and the regulatory authorities of findings that could adversely affect the safety of subjects, impact on the conduct of the study, or alter the IEC/ IRB approval/favorable opinion of the study. In addition, the sponsor and/or the appointed representative(s), will expedite the reporting to all concerned investigators, to the IEC(s)/IRB(s), where required, and to the regulatory authorities of all adverse reactions that are both serious and unexpected.

Details of the procedures to be followed if a pregnancy occurs are also provided in Section 7.4.4.

Documentation and Reporting of SUSARs

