10.4 Safety Evaluation

All safety assessments, including AEs, PEs, VS and clinical laboratory evaluations, where indicated, will be presented using descriptive statistics for each vaccine group of UB-612. Data will be summarized for each vaccine group and overall.

Solicited Adverse Event

Solicited AEs recorded on e-diary will be summarized by the severity grading scales by vaccine groups. Numbers and percentages of subjects experiencing each adverse event will be presented for each symptom severity by study groups. Summary tables showing the occurrence of any local or systemic adverse event overall and at each time point will also be presented.

Adverse Event

This analysis applies to all adverse events occurring during the study, recorded in AE eCRF, with a start date on or after the date of vaccination. AEs occurring during the study will be coded using MedDRA version 23.0 which is consistent with the V-122 phase I main study. The adverse events will then be grouped by MedDRA preferred terms into frequency tables according to system organ class.

All reported adverse events, as well as adverse events judged by the investigator as at least possibly related to study vaccine, will be summarized according to system organ class and preferred term within system organ class. When an adverse event occurs more than once for a subject, the maximal severity and strongest relationship to the vaccine group will be counted.

Separate summaries will be produced for the following categories, such as serious adverse events and AEs related to UB-612 vaccine will be presented. Data listings of all adverse events will be provided by subject.

Physical Examination

All physical examination findings will be listed and summarized by time point and study vaccine group. Shift table will be also presented, if appropriate.

Vital Signs

All vital sign findings will be listed and summarized by time point and study vaccine group.

Laboratory Evaluations

Laboratory safety data will be analysed descriptively by time point and study vaccine group. Shift table for laboratory data will be shown by visit using categorization of laboratory according to local laboratory's normal reference range.

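### V-123 contradicts itself on how long unsolicited adverse events are collected: 28 days in section 9.5.4.2, to Day 85 or without that limit elsewhere

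*Supplement*

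**What the plan says.** All references are to the V-123 protocol unless stated.

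**The 28-day rule.** Section 9.5.4.2: "Information of unsolicited symptoms/AEs will be collected until 28-day follow-up period after each vaccination", explained as "i.e. day of vaccination and 27 subsequent days) and reported at each visit".

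**Rules that run to Day 85 or carry no 28-day limit.**
- Section 7.1, and the study design part of the synopsis: "All adverse events and serious adverse events will be monitored from Visit 1 (Day 1) until Visit 3 (Day 85".
- Section 8.3, Visit 3 (Day 85), using the same instruction as Visit 2: "Record and report adverse or serious adverse event if any has occurred since the previous visit".
- Section 9.5.5: "In this study, all AEs/SAEs will be recorded after vaccination".
- Section 9.5.5.9: "All AEs occurring during the study must be documented on the relevant CRF pages".
- The schedule in section 7.2 marks AEs/SAEs at all three visits.

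**Planned use of the data.**
- Synopsis, Statistical Analysis: "AEs till Day 85 will be presented with number and percentage by system organ class, preferred term, and study vaccine groups".
- Section 10.4, where the last word of the sentence, naming the booster injection, is left off here: "This analysis applies to all adverse events occurring during the study, recorded in AE eCRF, with a start date on or after the date of".
- Section 6.4 lists AESIs, MAAEs and SAEs over the study period as a secondary safety endpoint.

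**The concern.** Two collection rules are in force for the same events, and a planned table depends on which one a site applies.

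The solicited-symptom diary closes after 7 days (section 9.5.4.1). A non-serious event starting after Day 28 can therefore reach the database only through AE recording at a visit. No visit is scheduled between Day 15 and Day 85, so events from both sides of Day 28 are elicited together at Visit 3. A coordinator who hears of a non-serious event that began on Day 40 must decide whether to enter it, and the protocol gives two answers. At that visit concomitant medication is recorded only for SAEs and AESIs (section 7.2, footnote c), which may nudge staff toward the narrower reading.

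The study is open-label, has no control group and has up to 20 subjects per group. The safety message rests on absolute percentages, so a reader must know how many days of observation lie behind them. The question also touches a listed endpoint. An MAAE is defined in section 9.5.5.4 as a kind of AE, so a non-serious MAAE after Day 28 falls outside the 9.5.4.2 window although section 6.4 counts it over the study period.

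**Working it through.** **1. Reproduce the stated window.** Day of vaccination plus 27 further days: 1 + 27 = 28 days. Vaccination is on Day 1, so the window is Day 1 to Day 28. The protocol's 28-day figure is reproduced.

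**2. Compare it with the table.** The AE table runs to Day 85.

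| Visit 3 takes place on | Days outside the 28-day window | Share of the period |
|---|---|---|
| Day 80 (lower visit window) | 80 − 28 = 52 | 52/80 = 65% |
| Day 85 (nominal) | 85 − 28 = 57 | 57/85 = 67% |
| Day 90 (upper visit window) | 90 − 28 = 62 | 62/90 = 69% |

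These are shares of days, not of events.

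**3. Set the rules side by side.**

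| V-123 section | Collection period for non-serious AEs |
|---|---|
| 9.5.4.2 | Day 1 to Day 28 |
| Synopsis (study design), 7.1 | Day 1 to Day 85 |
| 8.3, Visit 3 | since the previous visit (nominally Day 15), no cut at Day 28 |
| 9.5.5 | after vaccination, no end stated |
| 9.5.5.9 | during the study |

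Section 9.5.4.2 is the only one of these with a 28-day limit.

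**4. Look at where the sentence may come from.** V-122 section 9.6.4.2 has the same sentence. There it fits: two doses 28 days apart give Days 0–27 and 28–55, which matches V-122's table of AEs to Day 56. V-123 gives one dose, yet still refers to each vaccination. V-205 section 9.5.5.2 collects unsolicited AEs during the study period. Text carried over from V-122 without adaptation is the likely explanation, though the documents do not say so.

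**5. Consequence under each reading.**
- Sites follow 9.5.4.2: 57 of 85 days are uncollected for non-serious AEs, and the table's label overstates its coverage.
- Sites follow the other sections: collection and table both run to Day 85, and the gap is 0.
- Practice differs between staff or subjects: ascertainment after Day 28 is uneven, and the table cannot show this.

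**The case against.** The best defence is that 9.5.4.2 is an outlier. The synopsis, 7.1, the schedule, the Visit 3 procedure, 9.5.5 (which follows directly) and 9.5.5.9 all point the other way, and a site following the visit checklist would record everything to Day 85. In addition, AEs in general to Day 85 are not a listed endpoint. The primary safety endpoints cover 7 days, the secondary ones cover SAEs, AESIs, MAAEs and laboratory changes, and the phrase about Day 85 stands only in the synopsis. AESIs and SAEs have their own collection provisions.

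Much of this stands, and it rules out two stronger readings:
- A reader might infer that V-123 collects unsolicited AEs for 28 days only, so that the Day 85 table is bound to undercount. Most of the protocol says otherwise. The undercount is conditional on sites following 9.5.4.2.
- A reader might infer that about two thirds of the AEs would be missing. That turns a share of days into a share of events. It needs both the 28-day reading and a constant onset rate, and the documents give no post-booster rate or time course. If onset clusters soon after vaccination, the loss is smaller.

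What does not stand is the idea that the conflict is harmless. The 28-day limit is an explicit operational rule in the section that defines unsolicited AEs, and no text subordinates it. Non-serious MAAEs have a definition but no separate collection window to protect them. The V-123 analysis plan is not among the documents, but an analysis plan could not restore events that were never recorded.

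**Conclusion.** The protocol is inconsistent, and section 9.5.4.2 is wrong as written against the rest of V-123. The effect ranges from none, if sites work to Day 85, to 57 of 85 days (67%; 65% to 69% across the Visit 3 window) without collection of non-serious unsolicited AEs, if they apply 9.5.4.2. In the second case the Day 85 AE table and the non-serious MAAE count could be too low, or ascertained differently before and after Day 28. The number of events affected cannot be estimated from the documents. The primary 7-day safety endpoints are unaffected. The point is worth correcting because the study has no control group and the correction costs almost nothing.

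**What to change.** Reconcile the sections so that one collection window applies.

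- **Simplest:** align 9.5.4.2 with the Day 85 monitoring already stated elsewhere, and refer to the single booster rather than to each vaccination. This takes one sentence, with no added visit or sample, since Visit 3 already asks for events since the previous visit.
- **Alternative:** keep 28 days for general unsolicited AEs and label the AE table with that window. Then the synopsis (study design and statistical analysis), 7.1, 8.3, 9.5.5, 9.5.5.9 and 10.4 must all be amended to match, and SAE, MAAE and AESI collection to Day 85 must be stated explicitly. This needs edits in several places.
- **If data are already collected:** report which rule sites applied, and label the general AE table with the window actually collected.
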